### 11.2 Sample Size:

Within one performance site, and assuming roughly 20% attrition and accounting for screen

failures, we are requesting to enroll up to 116 (58 per arm) participants in order to evaluate a final sample of 85 (42-43 per arm).

### 11.3 Total number of subjects requested (including records and specimens):

116

### 11.4 If you are recruiting by study arm, please identify the arms of the study and how many subjects will be enrolled in each arm

Across one performance site, up to 116 patients will be randomized 1:1 to the two treatment arms (PBMT and Sham PBMT).

### 11.5 Please provide a justification for your sample size

Due to the accepted feasibility/pilot nature of this study, we understand that the proposed study may not be appropriately powered. Assuming a moderate effect size of .15 and a significance level of 5%; in the event we are able to enroll 116 participants (85 post-attrition) we will achieve 80% power. If we are able to enroll 135 participants (108 post-attrition), we will achieve 90% power. Power was calculated using the linear multiple regression module within G\*Power (Erdfelder, Faul, & Buchner, 1996).

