Taken as a whole, PBMT is a promising avenue for increasing overall performance by enhancing recovery processes, self-reported DOMS and fatigue, and potentially positively affecting behavioral health in the Special Operator population. We will conduct a single-blinded randomized-control trial with sham control to investigate the effectiveness of providing PBMT post physical training in a SOF population, thus translating this cutting-edge research to application in the THOR3 setting.

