#### Sham PBMT Arm:

Sham PBMT will be provided by a trained study team member. Sham PBMT will be delivered in the same manner as indicated for the PBMT process above, but the device will stay in standby mode (i.e., the treatment mode will not be turned on). As infrared light is invisible to the naked eye, the only visible difference between treatment and standby modes is the presence of a few tiny amber lights (these lights are on during treatment mode).

The inclusion of sham PBMT will ensure all participant treatment procedures remain the same, with the exception of emission of photons (active treatment), thus, allowing for contribution of any differences between groups to be credited to the use of PBMT.

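### The 80% and 90% power in section 11.5 are not the power of the PBMT-versus-sham comparison

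*Combined protocol and SAP*

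**What the plan says.** Section 11.5 opens with a caveat about the pilot character of the study: "we understand that the proposed study may not be appropriately powered". It then gives two power statements without further qualification. The first begins "Assuming a moderate effect size of .15 and a significance level of 5%; in the event we are able to enroll 116 participants", which it takes to leave 85 after attrition, and claims 80%. The second reads "If we are able to enroll 135 participants (108 post-attrition), we will achieve 90% power". On method it says "Power was calculated using the linear multiple regression module within" G\*Power. It does not say whether .15 is f², f, R² or d, which outcome is meant, how many predictors the model holds, or which of them are tested.

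Section 11.2 fixes the request: "we are requesting to enroll up to 116 (58 per arm) participants in order to evaluate a final sample of 85 (42-43 per arm"). Sections 11.3 and 11.4 repeat the 116, and in 11.4 participants are "randomized 1:1 to the two treatment arms".

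The question the trial asks is in section 9.2, "to investigate the effectiveness of providing PBMT post physical training in a SOF population", and in the Sham PBMT Arm text of section 10.1, where the sham is justified as "allowing for contribution of any differences between groups to be credited to the use of PBMT".

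Sections 11.1 and 11.6 plan generalized additive models for the 3-week change and multi-level models for the Oura Ring data. Section 11.6 sets two-tailed tests at 0.05. Control variables enter in the sensitivity analyses and are to be chosen after the data are seen. Neither section lists the predictors of the main model or describes a joint test of several predictors.

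**The concern.** In a two-arm trial the treatment effect is a single coefficient, tested on 1 df. Adding covariates to the model changes the residual degrees of freedom, but not the number of terms tested. A sample-size justification should give the power of that test. An effect size of .15 called moderate, taken from a multiple-regression module, suggests f² = .15. For one tested coefficient that value would need far fewer than 85 participants for 80% power. The stated sizes therefore point to a test of several predictors together.

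If so, the 80% and 90% say how likely the trial is to find that a set of predictors jointly explains something. They do not say how likely it is to find a difference between PBMT and sham. A reader faced with a null result could not use section 11.5 to judge what difference the trial was able to detect.

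**Working it through.** **Inputs.** Effect size .15, alpha 0.05, 80% at 85 and 90% at 108, fixed-model linear multiple regression (section 11.5). Two arms at 1:1 (section 11.4), 42 and 43 evaluable (section 11.2). Two-tailed tests (section 11.6).

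**Formula.** With u predictors tested in a model of p predictors, power is the probability that a noncentral F with df1 = u, df2 = N − p − 1 and noncentrality λ = f² × N exceeds the central F critical value at 0.05.

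**Step 1: reproduce the plan's figures.** Take f² = .15 with all predictors tested (u = p).

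| Predictors tested | Smallest N for 80% | Smallest N for 90% |
|---|---|---|
| 1 | 55 | 73 |
| 2 | 68 | 88 |
| 3 | 77 | 99 |
| **4** | **85** | **108** |
| 5 | 92 | 116 |
| 6 | 98 | 123 |

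For four predictors λ = .15 × 85 = 12.75 with 4 and 80 df, and power is 80.3% (79.7% at N = 84). At 108, λ = 16.2 with 4 and 103 df, and power is 90.1% (89.8% at N = 107). Both stated sizes are exact minima for four tested predictors and for no other number. Adding untested covariates (up to 12 predictors in all) leaves 85 and 108 unchanged. Reading .15 as R² comes close only with six jointly tested predictors (84 and 106), which is again a multi-df test.

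**Step 2: the arm comparison on 1 df, two-sided 0.05.**

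| Reading of .15 | f² | Power at 85 | Power at 108 |
|---|---|---|---|
| f² | 0.1500 | 94.2% | 97.9% |
| R² (.15/.85) | 0.1765 | 96.9% | 99.1% |
| f (.15²) | 0.0225 | 27.7% | 33.9% |
| d (.15²/4) | 0.0056 | 10.5% | 12.1% |

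None is near 80% and 90%. With f² = .15, holding up to 10 predictors in the model changes the 1-df power by less than 0.001.

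**Step 3: which way the error runs.** At 1:1, d = 2√f². If all of .15 belongs to treatment, d = 2√.15 = 0.775, and the plan understates its power. If .15 is a total shared with three covariates, the treatment share is not given. The table assumes shares s, four uncorrelated predictors and partial f² = s × .15.

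| Assumed treatment share | Power at 85 | Power at 108 |
|---|---|---|
| 25% | 42% | 51% |
| 50% | 70% | 80% |
| 75% | 86% | 93% |
| 100% | 94% | 98% |

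The share at which arm power equals the stated figure is 63% at 85 (partial f² 0.0946/.15 = 0.631) and 66% at 108 (0.0991/.15 = 0.661).

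**Step 4: what the trial can detect.** Unadjusted two-sample comparison, two-sided 0.05:

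- 85 evaluable (42/43): standardised difference 0.615 for 80% power, 0.712 for 90%.
- About 93 evaluable (46/47; 116 × 0.8 = 92.8, with no loss beyond 20% attrition): 0.587 for 80%.
- 108 evaluable (54/54): 0.544 for 80%, 0.630 for 90%.

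**Step 5: the 90% scenario.** 135 × 0.8 = 108, so it rests on 135 enrolled. To keep 108 out of the 116 requested, loss could be at most 1 − 108/116 = 6.9%, against the roughly 20% assumed in section 11.2.

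**The case against.** The strongest reply is that nothing has been miscalculated. For four tested predictors the module does return 85 and 108, and what is missing is a statement of the inputs. Sections 11.1 and 11.6 list no predictors for the main model, so they do not rule out a four-term model. This is fair as far as it goes: the software output is right for its inputs. But even if the main model held four terms, its treatment term would still be tested on 1 df, and the figures would still not describe that test.

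Alpha could also be varied. At 0.05/6 a 1-df test with f² = .15 has power near 80% at 85 and near 91% at 108. Section 11.5 states 5%, however, and section 11.6 plans a false discovery rate adjustment of secondary P-values, not that correction. The smallest size for 90% would then be 106, not 108.

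Third, no shortfall is shown. If .15 is the treatment effect alone, the trial has more power than it claims, and the treatment shares in Step 3 are assumptions that no section supplies. That stands, and no shortfall is claimed here.

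Last, section 11.5 concedes possible underpowering, the aims in section 9.3 are descriptive, and the 135 scenario is worded conditionally. These points reduce the consequence. They do not tell the reader to which test or difference the 80% and 90% apply.

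**Conclusion.** The point holds and should be fixed. At the stated 5% level, 80% at 85 and 90% at 108 match no 1-df reading of .15, so they are not the power of the PBMT-sham comparison. Under f² = .15 the arm comparison has 94% and 98% if the whole effect is treatment. It falls below the stated figures if treatment accounts for less than about 63% (at 85) or 66% (at 108) of a shared .15. The documents do not give that share, so the direction of the error is unknown.

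That four predictors were entered is an inference from the exact match at both sizes. The conclusion does not depend on it, because the nearest alternative is also a multi-df test that the plan lacks. The detectable differences assume a single continuous 3-week change score, no covariate adjustment and no multiplicity adjustment.

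**What to change.** Keep the sample size and the pilot caveat. In section 11.5 replace the two power sentences with a statement about the arm coefficient, for example: *With 85 evaluable participants (42/43) and two-sided alpha 0.05, an unadjusted comparison of [named outcome], without false discovery rate adjustment, has 80% power for a standardised PBMT-sham difference of 0.615; covariate adjustment may improve this.*

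Delete the 108-evaluable sentence, or label it: *Hypothetical, beyond the 116 requested: 135 enrolled (108 evaluable) would give 80% power for a standardised difference of 0.544 and 90% power for 0.630.*

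Sections 9.3, 11.1 and 11.6 single out no outcome. The team must either name one and carry it into those sections, or say in 11.5 that the figure applies to any single continuous 3-week change score tested at an unadjusted 0.05. The cost is wording only: no extra participants and no change to conduct.

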### 11.6 Data Analysis Plan: Complete description: Background, Objectives, Design, Step by Step how the project is going to be done, Data analysis plan:

Descriptive statistics will report location and scale in terms of mean and standard deviation for normally distributed variables, median and interquartile intervals for ordinal metric variables, and in terms of proportion and size for categorical variables. Descriptive statistics will be reported for baseline demographic and clinical characteristics at an overall level and by initial treatment group.

Statistical analyses will use generalized additive models predicting the change in outcome measures at 3 weeks relative to baseline for all measures except Oura Ring data. Oura Ring data will be aggregated by averaging readings across each 24-hour period and will be modeled using multi-level models incorporating random effects. Sensitivity analyses will be performed on longitudinal data for each outcome metric and will include multi-level models incorporating random effects as well as control variables to account for patient characteristics. Exact selection of control variables will be guided by observed differences within final collected data as well as relevant clinical expertise.

Hypothesis tests will be two-tailed and statistical significance will be considered at the putative threshold ( $\alpha=0.05$ ). Any secondary P-values will be subject to a false discovery rate adjustment in keeping with best statistical practices. Multilevel models will incorporate random effects to account for repeated measures, using distribution families and link functions appropriate for the outcomes of interest, determined using quantile-quantile (QQ) plots analyzed for best model fit. All statistical analyses will be performed using the R Programming language.

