#### **Appendix D Baseline Data Collection CRF:**

Collects relevant baseline research data.

- Self-reported medical history
- Current military & work status
- DVPRS
- QPAR
- VAS
- Borg Perceived Exertion Scale
- Elloumi fatigue scale
- Fitzpatrick Phototyping Scale
- Body measurements
- CMJ
- Isometric/Isokinetic Strength

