#### **Appendix E Follow-Up Data Collection CRF:**

Collects relevant follow-up research data.

- VAS
- Borg Perceived Exertion Scale (3-week follow-up only)
- Elloumi fatigue scale (only at 3-week follow-up)
- CMJ
- Isometric/Isokinetic Strength (3-week follow-up only)
- Adverse Event (AE) assessment

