## 11.0 Statistical/Data Analysis Plan

### 11.1 Statistical Considerations:

List the statistical methods to be used to address the primary and secondary objectives, specific aims, and/or research hypotheses. Explain how missing data and outliers will be handled in the analysis. The analysis plan should be consistent with the study objectives. Include any subgroup analyses (e.g., gender or age group). Specify statistical methods and variables for each analysis. Describe how confounding variables will be controlled in the data analysis

Descriptive statistics will report location and scale in terms of mean and standard deviation for normally distributed variables, median and interquartile intervals for ordinal metric variables, and in terms of proportion and size for categorical variables. Descriptive statistics will be reported for baseline demographic and clinical characteristics at an overall level and by initial treatment group.

Outliers will be removed if determined to be erroneous based on relevant clinical expertise. Confounding will be principally controlled by randomization. In regards to the treatment of missing data, Oura Ring data will be analyzed despite presence of missing data at any point; with regards to non-continuous outcomes, data will be analyzed only if baseline and the 3-week follow-up are both present. In the event of missing data for a mid-point follow up (i.e., not baseline or the 3-week follow up), said patient will still be included in all models.

Statistical analyses will use generalized additive models predicting the change in outcome measures at 3 weeks relative to baseline for all measures except Oura Ring data. Oura Ring data will be aggregated by averaging readings across each 24-hour period and will be modeled using multi-level models incorporating random effects. Sensitivity analyses will be performed on longitudinal data for each outcome metric and will include multi-level models incorporating random effects as well as control variables to account for any differences explained by a selection of patient characteristics (such as body weight, etc.).

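### The 3-week change models state no baseline term, which gives up some precision at no cost in data, and the sensitivity-model covariates are to be picked partly from the final data

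*Combined protocol and SAP*

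**What the plan says.** Sections 11.1 and 11.6 give the same main analysis for all outcomes other than the Oura Ring data: "Statistical analyses will use generalized additive models predicting the change in outcome measures at 3 weeks relative to baseline". No predictor is listed for these models. On adjustment, section 11.1 says: "Confounding will be principally controlled by randomization".

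Covariates appear only in the sensitivity analyses, which are multi-level models of the longitudinal data. Section 11.1 says these will include "control variables to account for any differences explained by a selection of patient characteristics" and offers body weight as its one example. Section 11.6 adds: "Exact selection of control variables will be guided by observed differences within final collected data as well as relevant clinical expertise".

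The baseline values exist. The baseline form (Appendix D, described in section 10.2 as "Collects relevant baseline research data") lists countermovement jump (CMJ), strength, VAS, Borg, Elloumi and DVPRS. On the follow-up form (Appendix E) strength is marked "Isometric/Isokinetic Strength (3-week follow-up only"), as are Borg and Elloumi, while CMJ and VAS carry no such limit. DVPRS is recorded daily in the activity log (Appendix F).

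On size, section 11.5 concedes that "we understand that the proposed study may not be appropriately powered".

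**The concern.** A change score subtracts the whole baseline value. That is the efficient correction only when the slope of the 3-week value on baseline is 1. When the slope is below 1, as it is with equal SDs and any correlation below 1, subtraction over-corrects and adds baseline noise to the outcome. Putting baseline in the model lets the data set the slope and removes that noise. Because the change already requires baseline, this needs no extra visit or participant.

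The comparison of mean change between randomized arms is unbiased with or without the term, so what is at stake is the width of the confidence intervals and the power. That matters in a study that doubts its own power and still plans two-tailed tests at 0.05.

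The second point is narrower. If covariates are chosen after looking at differences in the final data, the sensitivity models are not fixed in advance and cannot serve as an independent check on the main result.

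**Working it through.** **The plan's own figures.** Section 11.5 uses an effect size of .15, a 5% level and the linear multiple regression module of G\*Power, and states 80% power at 85 evaluable and 90% at 108. Read .15 as f², with noncentrality f²·N and k tested predictors on k and N−k−1 degrees of freedom:

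| k | Power at N = 85 | Power at N = 108 |
|---|---|---|
| 1 | 0.942 | 0.979 |
| 3 | 0.845 | 0.928 |
| 4 | 0.803 | 0.901 |
| 5 | 0.764 | 0.875 |

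The stated figures reproduce with four tested predictors. The plan names none of them.

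**Inputs for the comparison.** From the documents: 85 evaluable, taken as 42 and 43 per arm (11.2), and a two-sided 5% test (11.6). Assumed: the correlation r, from 0.3 to 0.9; a true difference of 0.5 SD; a continuous outcome with a linear relation to baseline; equal SDs at the two visits unless stated otherwise.

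**Variance.** With SD = 1 at both visits:

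- change score: residual variance 2(1−r)
- change score with linear baseline: residual variance 1−r²
- ratio: (1−r²) / [2(1−r)] = (1+r)/2

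**Power.** The standard error is √[residual variance × (1/42 + 1/43)], and √(1/42 + 1/43) = 0.217. Degrees of freedom are 83 without baseline and 82 with it. Worked case, r = 0.5:

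- without baseline: residual variance 1.00, noncentrality 0.5/0.217 = 2.30, power 0.625
- with baseline: residual variance 0.75, noncentrality 0.5/(0.217 × √0.75) = 2.66, power 0.749

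| r | Variance ratio | Power at 0.5 SD, without → with | Difference detectable at 80% power (SD), without → with |
|---|---|---|---|
| 0.3 | 0.65 | 0.486 → 0.666 | 0.728 → 0.587 |
| 0.5 | 0.75 | 0.625 → 0.749 | 0.615 → 0.533 |
| 0.7 | 0.85 | 0.837 → 0.891 | 0.476 → 0.439 |
| 0.8 | 0.90 | 0.950 → 0.967 | 0.389 → 0.369 |
| 0.9 | 0.95 | 0.9991 → 0.9995 | 0.275 → 0.268 |

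**The .15 read as the arm contrast alone.** If .15 is f² for treatment arm on the change score, noncentrality is 0.15 × 85 = 12.75 and power without baseline is 0.942 at every r. With baseline, noncentrality becomes 12.75 / [(1+r)/2], and power is 0.992, 0.983, 0.969, 0.961 and 0.952 for r = 0.3, 0.5, 0.7, 0.8 and 0.9. This one-predictor reading is not the one that gives the plan's 80%.

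**Unequal SDs.** Let k now be the 3-week SD divided by the baseline SD. The change score has variance k² + 1 − 2rk and the adjusted analysis k²(1−r²), in baseline-variance units. The difference is (1−rk)², which is never negative. At r = 0.7 the ratio is 0.628 for k = 0.8 (a 37% cut) and 0.966 for k = 1.2 (a 3% cut).

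**Linear or smooth.** In 8,000 simulated normal trials per r with a 0.5 SD effect, the mean estimate was 0.50 without baseline, with linear baseline and with a three-term cubic. The variance ratio to unadjusted change, for r = 0.3, 0.5, 0.7, 0.8 and 0.9, was 0.667, 0.760, 0.865, 0.912 and 0.955 (linear) and 0.681, 0.780, 0.888, 0.939 and 0.981 (cubic). The curve costs a little more than the line.

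**The case against.** The strongest reply is that silence is not exclusion. The plan names no predictor at all for these models, not even treatment arm. An additive model with only a two-level factor has nothing to smooth, and the power figures fit four predictors rather than one. Baseline may therefore have been intended. That is possible, and it stands as a caveat. But no reader of the plan could tell, and an unstated term is not pre-specified. One sentence resolves it either way.

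Second, the gain depends on assumed values and may be trivial. This also stands in part. At r = 0.9 there is next to nothing to gain. In settings where rk is close to 1 the finite-sample cost can cancel it: 20,000 simulated trials with the 3-week SD 20% larger gave variance ratios of 1.011 for a linear term at r = 0.8, and 1.005, 1.036 and 1.009 for an unpenalised cubic at r = 0.7, 0.8 and 0.9. Those losses are very small beside the possible gains, and the documents give no reason to think every outcome has so high a correlation.

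Third, the aims are descriptive and section 11.5 calls the study a feasibility or pilot one. That limits the consequence of lost power, but it is not a reason to discard information already collected.

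Fourth, section 11.6 also relies on clinical expertise for covariate choice, and the main models are not touched. Both are true, which is why that point is secondary.

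**Conclusion.** The concern holds. As written, the main models for all non-Oura outcomes state no baseline term, and the covariates of the sensitivity models are left to be chosen partly from the final data.

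This should be changed, but it does not threaten the validity of the randomized comparison. The likely benefit ranges from substantial for outcomes that track baseline loosely to negligible for those that track it very closely. Where each outcome falls cannot be settled from the documents. The figures are for continuous outcomes; the gain for the rating scales (VAS, Borg, Elloumi, DVPRS) has not been quantified. All of this takes the plan's silence at face value: if baseline was among the predictors behind the sample size, the defect is only that it was not written down.

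**What to change.** In sections 11.1 and 11.6, add:

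> Each 3-week change model (all measures except Oura Ring data) will include treatment arm and the baseline value of that outcome.

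Say whether baseline enters as a linear or a smooth term.

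For the sensitivity models, replace selection from observed differences with a short named list of baseline covariates, for example body weight, fixed before outcome data are examined by arm.

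In the longitudinal sensitivity models, use an outcome's own baseline as a covariate only if baseline is not also one of the repeated responses. Strength, Borg and Elloumi are listed only at baseline and 3 weeks, so a repeated-measures model for them must treat baseline as a response and should not adjust for it as well. For CMJ and VAS (weekly) and DVPRS (daily), state which role baseline takes.

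The cost is wording in the analysis plan. No new data are needed. A linear term uses one degree of freedom per model and a smooth term slightly more.
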